3.4.6 Off-study

Research participants will be discontinued from participating in this study for the following circumstances:

- ◆ There is radiographic evidence of pancreatic cancer recurrence.
- ◆ Serious vaccine related adverse events occur.
- ◆ The vaccine supply is exhausted.
- ◆ The research participant is noncompliant, is unable to comply with the treatment plan, or requests withdrawal.
- ◆ The research participant is receiving concomitant immunotherapy, chemotherapy, radiotherapy, or other biological or gene therapy.

If determined to be off-study, the research participant will be followed for 28 days after the administration of the last vaccine for toxicities related to the vaccine, or longer, if vaccine-related toxicities occur. Whenever possible, the research participant will be asked to have the tests indicated for the day 28 visit as the off-study visit, unless this was done within 28 days of the off-study date.

If the research participant consents there will be a lifelong follow-up through participation in [name] study, IRB # NA_00036444 (SKCCC J0248) entitled, Long term follow-up of patients who received lethally irradiated allogeneic pancreatic tumor cells transfected with the GM-CSF gene.

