9. If not previously enrolled on IRB # NA_00036444 (SKCCC J0248) entitled, Long term follow-up of patients who received lethally irradiated allogeneic pancreatic tumor cells transfected with the GM-CSF gene, the research participant will be encouraged to join the long-term follow-up study.
10. Collect and review the diary of prime vaccine #2. Provide new diary.

Day 28 after Prime Vaccine #3 (-3 /+ 14 days)

1. A leukapheresis for in vitro studies will be encouraged. If the research participant refuses a leukapheresis, approximately 200 cc of blood will be drawn.
2. Vital signs.
3. Assessment for toxicities and vaccine site reactions from previous vaccinations, and medications.
4. Photograph of vaccine sites or reactions (if clinically indicated)
5. Several psychosocial and symptom instruments, including: quality of life, hope, and trust surveys. (See appendices for copies of the instruments).
6. If not previously enrolled on IRB # NA_00036444 (SKCCC J0248) entitled, Long term follow-up of patients who received lethally irradiated allogeneic pancreatic tumor cells transfected with the GM-CSF gene, the research participant will be encouraged to join the long-term follow-up study.
7. Collect and review the diary.

3.4.1.4. Both Cohorts- Semi-annual or Annual Boost Vaccinations after the previous vaccination:

In the event that a research participant has evidence of persistent vaccine-related responses (including, but not limited to: vaccine site flares such as recurrent erythema, induration, and pruritus at previous vaccine administration sites; urticaria) occurring at the frequency of more than once in the previous three months, the research participant may choose to delay the semi-annual or annual boost vaccination for up to one year after the last vaccine-related response. If the research participant chooses to delay the semi-annual or annual vaccinations due to persistent vaccine-related responses, evaluations to include: research and standard blood samples; clinical evaluation; CT scans of the abdomen, chest, and pelvis; and surveys, as described in “Day-28 to Day 0” below may be obtained semi-annually or annually.

The research participant may also choose to continue to receive the semi-annual or annual boost vaccinations per protocol with evidence of persistent vaccine-related responses. Research participants experiencing urticaria must wait at least one month since the last hive before receiving another vaccine.

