Data and samples may be obtained from Day-28 to Day 0

1. A clinical evaluation to include vital signs, ECOG status, weight, review of systems, physical examination, and toxicity evaluation.

2. CT scans of the abdomen, pelvis, and chest. If the CT scan is not done at Hopkins, the research participant must provide the report and a copy of the scans. If the research participant is allergic to the CT scan contrast or is contraindicated, a non-contrast CT of the chest and a MRI of the abdomen and pelvis will be obtained.
3. A leukapheresis for in vitro studies will be encouraged. If the research participant refuses a leukapheresis, approximately 200 cc of blood will be drawn. As of Amendment #8, research bloods are no longer required to be collected.
4. Blood testing to include CBC/diff, absolute eosinophils, absolute neutrophils, absolute lymphocytes, comprehensive chemistry panel including electrolytes, albumin, BUN, creatinine, AST, ALT, total bilirubin, and alkaline phosphatase, amylase, and CA 19-9.
5. Research blood: 20 cc for serum banking. As of Amendment #8, research bloods are no longer required to be collected.
6. Pregnancy test for women of childbearing potential. Urine pregnancy test preferred.
7. If not previously enrolled on IRB # NA_00036444 (SKCCC J0248) entitled, Long term follow-up of patients who received lethally irradiated allogeneic pancreatic tumor cells transfected with the GM-CSF gene, the research participant will be encouraged to join the long-term follow-up study.

Day 0

1. Administration of vaccine (Topical lidocaine-based anesthetic may be placed about 1-2 hours prior to planned vaccine administration time to the intended vaccine sites.)
2. Vital signs before and after vaccine administration
3. Photograph of vaccine sites (if clinically indicated)
4. Assessment for toxicities
5. Monitor for 30 minutes after vaccine administration
6. Tetanus toxoid boost if last tetanus vaccination > 10 years. Tetanus/diphtheria (Td) may be substituted if tetanus alone is not available. If both are not available, no tetanus vaccine will be administered.

Day 28 after Boost Vaccine (-3/ + 14 days)

1. A leukapheresis for in vitro studies will be encouraged. If the research participant refuses a leukapheresis, approximately 200 cc of blood will be drawn. As of Amendment #8, research bloods are no longer required to be collected.
2. Assessment for toxicities and vaccine site reactions from previous vaccinations, and medications.

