3. Photograph of vaccine sites or reactions (if clinically indicated)
4. If not previously enrolled on IRB # NA_00036444 (SKCCC J0248) entitled, Long term follow-up of patients who received lethally irradiated allogeneic pancreatic tumor cells transfected with the GM-CSF gene, the research participant will be encouraged to join the long-term follow-up study.

If the research participant is unable to return to Johns Hopkins for the day 28 after boost visit, effort will be made to obtain information for this visit. Data may be obtained regarding toxicity and vaccine site reactions by study clinician contact with the research participant, his/her family, or health care providers. The surveys may be mailed to the research participant's home with a stamped return envelope. Fax and electronic correspondence for the diaries and surveys is also

acceptable. Arrangements may be made for the research samples to be obtained locally and shipped to the Hopkins' [name] Lab.

Off-study

1. A clinical evaluation to include vital signs, ECOG status, weight, review of systems, physical examination, measurement of vaccine sites and toxicity evaluation.
2. CT scans of the abdomen, pelvis, and chest. If the CT scan is not done at Hopkins, the research participant must provide the report and a copy of the scans. If the research participant is allergic to the CT scan contrast or the contrast is contraindicated (as in the case for renal insufficiency), a non-contrast CT of the chest and a MRI of the abdomen and pelvis will be obtained.
3. A leukapheresis or approximately 200 cc of peripheral blood will be obtained for in vitro studies. As of Amendment #8, research bloods are no longer required to be collected.
4. Research blood: 20 cc for serum banking. As of Amendment #8, research bloods are no longer required to be collected.
5. Blood testing to include CBC/diff, absolute eosinophils, absolute neutrophils, absolute lymphocytes, comprehensive chemistry panel including electrolytes, albumin, BUN, creatinine, AST, ALT, total bilirubin, alkaline phosphatase, and CA 19-9.
6. Assessment of vaccine sites. This will include: number of sites that have erythema, induration, pruritus, and tenderness; and measurement of induration and erythema of largest vaccine site.
7. Assessment of toxicities (Information may include evaluations made by the local health care provider.)

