We are also interested in investigating the effect of vaccine boosts on recurrence free survival (PFS). Patients who are treated at Johns Hopkins will be followed every 3 months and evaluated for recurrence. However, the standard of care follow-up varies from institution to institution. In order to prevent biasing our results, it is necessary to coarsen the follow-up interval so that every individual is evaluated at the same time points regardless of the institution. For example, if the only visits held in common among all patients were the semi-annual exams prior to vaccine boosting, it would be necessary to only consider the status of the JH patients at those two time points regardless of recurrence information gained from the additional 2 visits. This coarsening of the data may cause an overestimation of PFS. In order to take into account both potential forms of bias, we will perform our analysis of PFS on the entire cohort as well as the subpopulation of patients from Johns Hopkins (estimated to be approximately 50% of the research participants). PFS will be defined as the time from the first vaccine until evidence of disease recurrence. If a patient withdraws from the study prior to being diagnosed with progressive disease, they will be censored at the date of their last follow-up visit. If an individual dies prior to being diagnosed with progressive disease, they will be considered to have progressed at the date of their last follow-up visit. This is a conservative estimate if we count the disease recurrence at the next planned visit then this will bias the PFS time upward. The PFS will be summarized using Kaplan-Meier curves and estimates of median PFS with 95% confidence intervals based upon Greenwood's formula. Due to potential causes of bias discussed earlier, the results will be considered extremely preliminary. If the PFS estimates for patients treated at Johns Hopkins appear to be lower than that of the population as a whole and the Johns Hopkins patients are followed at more frequent intervals than the other patients, then this indicate that an overestimation of PFS may exist. No formal comparison is planned due to the small sample size. Such results could affect the future planning of follow-up treatment for patients in subsequent trials.

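### The off-study visit has two incompatible definitions (with CT and safety laboratory tests in 3.4.1.4, without either in 3.4.6), and PFS may be censored at an exit with no imaging

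*Combined protocol and SAP*

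**What the plan says.** Two parts of the protocol describe the same visit.

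- **3.4.1.4, off-study block.** The list includes a clinical evaluation, "CT scans of the abdomen, pelvis, and chest", a CBC with differential, and a chemistry panel that ends with "total bilirubin, alkaline phosphatase, and CA 19-9". It also has research blood, vaccine-site assessment and toxicity assessment. The list need not be repeated if a protocol visit within 28 days already obtained those assessments and samples. If the participant cannot return, medical records are sought, and toxicity and disease status may come from contact with the participant, family or health care providers.
- **3.4.6.** Where possible, "the research participant will be asked to have the tests indicated for the day 28 visit as the off-study visit". This is waived if it was done within 28 days of the off-study date.

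The clinical content of the day 28 visit after a boost is "Assessment for toxicities and vaccine site reactions from previous vaccinations, and medications", with photographs if indicated. Leukapheresis or about 200 cc of research blood is also listed, with the note "As of Amendment #8, research bloods are no longer required to be collected".

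For PFS, 4.3.1 ties the censoring of withdrawals to a follow-up visit: "If a patient withdraws from the study prior to being diagnosed with progressive disease, they will be censored at the date of their last" such visit. Section 5.1 defines recurrence by CT.

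**The concern.** Two staff members who each follow the protocol could run different exit visits, one with CT and a laboratory panel and one with neither. The participants affected leave for reasons other than recurrence already seen on imaging: withdrawal, noncompliance, a serious vaccine-related event, other therapy, or exhausted vaccine supply.

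The PFS rule makes this matter for the analysis. The event can be established only by imaging, but the censoring date is set by a visit, and nothing in 4.3.1 requires that visit to include imaging. Time between the last negative scan and an unscanned exit could then be counted as recurrence free although nobody looked.

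**Working it through.** The documents give no figure to reproduce. The check is a comparison of text, followed by the effect on the Kaplan-Meier estimate.

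**Step 1. The two lists side by side.**

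| Item | Off-study list, 3.4.1.4 | Day 28 tests, used by 3.4.6 |
|---|---|---|
| Clinical evaluation (ECOG, weight, review of systems, examination) | listed | not listed |
| CT abdomen, pelvis, chest | listed | not listed |
| CBC with differential, chemistry panel | listed (amylase, in the baseline and boost panels, is absent) | not listed |
| CA 19-9 | listed | not listed |
| Leukapheresis or about 200 cc research blood | listed, not required since Amendment #8 | listed; after boosts not required since Amendment #8 |
| Toxicity and vaccine-site assessment | listed | listed |

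The right-hand column holds for the visit after the third prime (3.4.1.3), the visit after a boost (3.4.1.4) and the Day 28 column of Table 3. Day 28 after the first or second prime is the next priming visit, whose list also has no CT and no clinical laboratory tests.

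**Step 2. The waivers.** In 3.4.6 a completed day 28 visit is enough. In 3.4.1.4 the earlier visit must have obtained the off-study assessments and samples, which a day 28 visit does not do.

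The schedule windows bound the age of the last protocol CT when the 3.4.6 waiver is used, leaving permitted delays aside:
- After a boost: CT up to 28 days before the vaccine, day 28 visit up to 28 + 14 = 42 days after it, exit up to 28 days later. Total: 28 + 42 + 28 = 98 days.
- After the third prime: the only scheduled CT precedes the first prime, and the primes are up to 31 days apart. Total: 28 + 31 + 31 + 42 + 28 = 160 days.

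For a later exit with only day 28 tests, the age of the last protocol CT can approach the boost interval, which was six months and is annual as of Amendment #9.

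**Step 3. Effect on PFS.** The Kaplan-Meier estimate is S(t) = Π(1 − d_j / n_j) over event times up to t, with d_j events among n_j at risk. Moving a participant's censoring date from the last negative scan to a later unscanned visit leaves every d_j unchanged and can only raise some n_j. Each factor stays the same or increases, so S(t) cannot fall. The shift is upward or nil. Its size depends on how many participants exit, when they were last imaged, and whether exit is related to recurrence. The documents give none of these.

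**The case against.** Much of the case on the other side stands.

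- Participants who leave for radiographic recurrence are already events. For the others, 5.1 has symptomatic patients evaluated for metastases, and 3.4.4 has outside scans and notes requested and Hopkins records accessed at least quarterly. Follow-up continues after exit with consent. These routes narrow the gap, but they depend on symptoms, outside care, record retrieval or consent, and they do not settle which list applies.
- Participants who withdraw or stop complying may attend neither version of the visit. That is fair, and it limits how much the choice of list matters for them.
- Section 4.3.1 plans to coarsen assessments to time points common to all patients, so an exit CT on an individual date may not count in the whole-cohort analysis. The last follow-up visit could also be read as one at which recurrence was evaluated. Both readings are possible, but the text states neither for censoring.

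A reader might infer three stronger things that the documents do not support.

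- **That day 28 has no blood draw at all.** Research blood is listed. What is missing is CT and clinical safety laboratory tests.
- **That a definite number of recurrences would be reclassified.** If exits fall at random between annual scans, the average chance of an undetected recurrence, the mean of 1 − exp(−ht) over 0 to 12 months with h = ln2/median, is 27.9%, 19.9% or 15.5% for assumed median PFS of 12, 18 or 24 months. Over 0 to 6 months it falls to 15.5%, 10.7% or 8.2%. The medians are assumptions, any count also needs an assumed exit rate, and about half the participants are expected to be Hopkins patients evaluated every 3 months. This is not an expected effect.
- **That laboratory data on participants removed for toxicity exist under one section only.** Related events are followed to resolution (6.1), and clinically indicated visits may include laboratory testing (3.4.1). The absence of laboratory tests at day 28 after a boost applies to every participant and belongs mainly to the general schedule.

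**Conclusion.** The contradiction is real and can be read directly from the protocol: 3.4.1.4 and 3.4.6 differ on clinical evaluation, CT, clinical laboratory tests and the waiver, and no sentence resolves it. The documents do not show which version was intended.

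The consequence is limited. Whether a participant who leaves without radiographic recurrence has a scheduled CT and laboratory panel at exit depends on the section followed, and other sources may fill part of the gap. For PFS, unverified time can count as recurrence free. The size is unknown and probably small, since 4.3.1 already treats these results as extremely preliminary and plans no formal comparison. The bias would be upward if exit is related to recurrence. The interim toxicity rule, based on 28 days from the first vaccine, does not rest on the off-study visit except for someone who leaves within that window.

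The conclusion needs no assumed rate. It rests on reading the last follow-up visit as any visit or contact, which 4.3.1 does not exclude.

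**What to change.** 1. Reconcile the off-study block of 3.4.1.4 with 3.4.6, including both waivers, into one off-study list, and have 3.4.6 refer to it. The content of that list is for the sponsor and investigator to decide; this review does not choose it.
2. In 4.3.1, censor PFS for participants without recurrence at the date of the last imaging assessment that showed none. For the coarsened whole-cohort analysis, use the last such assessment on the common schedule. A visit, telephone contact or record without imaging then never extends recurrence-free time, whichever off-study list is adopted.

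The cost is a few lines of wording and, for PFS, use of imaging dates in place of visit dates. Stated PFS may become slightly less favourable. The second change removes unverified time but does not correct for participants who leave because they are declining. Reporting reasons for exit and the interval from last imaging to exit would let a reader judge that.

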3.5 Management of Toxicities

Local vaccine site reaction may be treated with topical applications of aloe vera or vitamin E gel or lotion. Significant local inflammation that is causing the research participant severe pain or is interfering with the activities of daily living may be treated with cold packs and oral analgesics. Local toxicities of pruritus at the vaccine sites and systemic pruritus may be treated with topical or oral diphenhydramine hydrochloride (Benadryl) or topical aloe vera. If oral diphenhydramine hydrochloride is used the recommended dose shall be 25-50 mg every four to six hours as needed for pruritus, not to exceed 300 mg/day. Cases of local ulceration should be manageable with local

wound care, with or without antibiotics. Severe local inflammation or significant clinical autoimmunity will be managed on a case by case basis.

4.0 Statistical Considerations

4.1 Sample Size

The primary statistical endpoint of this study is to evaluate the safety and feasibility of vaccine boosting with lethally irradiated allogeneic pancreatic tumor cells transfected with the GM-CSF gene. Among patients who have previously been treated with the vaccine, the cohort is limited to those who continue to have no disease recurrence for at least 1 year after treatment. Currently, there are three potentially eligible patients from the original phase I study, and 14 from the phase II study. A total of up to 17 previously treated patients will be eligible to continue to receive vaccine treatment in the form of semi-annual boosts. The second cohort of vaccine naïve patients who have been recurrence free for at least 28 days following adjuvant therapy will be given three priming vaccines each a month apart, followed by semi-annual vaccine boosts in order to determine the feasibility of administering the vaccination to vaccine naïve patients and to obtain initial estimates of the efficacy of such treatment with respect to prolonging disease-free status. As of Amendment #9, participants will be switched to annual vaccinations. We will base our determination of feasibility by estimating the proportion of patients with a dose limiting toxicity (DLT) within 28 days of the first vaccine treatment. Between 20 and 45 vaccine naïve patients will be included. An initial group of 20 patients will be recruited and an interim analysis will be performed in order to guard against excessive toxicities relating to treatment. No DLTs have been observed in either the phase I or II studies. If there is significant evidence that more than 10% of the vaccine naïve patients have dose limiting toxicities within 28 days of the first vaccination, then the trial will be halted. If 6 out of 20 of the initial patients have DLTs, the lower bound of the exact 95% confidence interval for the proportion of patients with a DLT is 11.89%. Therefore, we will halt the trial due to excessive toxicity at the interim analysis if 6 or more patients have a DLT within the first 28 days of their first vaccine. Otherwise, an additional 20 vaccine naïve patients will be accrued. If 20 patients are accrued, the maximum width of the 95% confidence interval estimate of the proportion of patients with a DLT is 0.438. If the full cohort of 40 patients is accrued, then the maximum width of the 95% confidence interval is 0.309.

The sample size was expanded to include a cohort of up to 45 vaccine-naïve research participants and 17 previously vaccinated research participants for a total sample up to 62 research participants.

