
who are vaccine naïve (30-45). For those patients who have received the vaccine, the boosts will be offered as a continuation of care. For those patients who are vaccine naïve, the feasibility of investigating the use of vaccine priming and boosting to prolong disease free status will be tested. Up to 100 patients may be consented to obtain the targeted accrual goal.

For research participants who have previously received the pancreatic cancer vaccine, the first vaccine boost will be given at least six months after the anniversary date of their last vaccination (+/- 30 days). Since the last vaccination date from the parent vaccine study for some subjects has occurred more than one year ago, they may establish a new semi-annual dates for vaccine boosting. As of Amendment #9, participants will be switched to annual vaccinations. One of the semi-annual or annual vaccine boost dates will be the same as their annual long term-follow-up visit date.

For research participants who are vaccine naïve, their first vaccine will be given at least 28 days after their last anti-cancer therapy. The vaccine naïve research participant will receive priming vaccinations once every month for a total of three vaccines, and then will receive the vaccine boosting on a semi-annual basis. As of Amendment #9, participants will be switched to annual vaccinations.

The vaccine will be administered once every six months (+/- 30 days) after the previous vaccine until the subject no longer meets the eligibility criteria, no longer wishes to participate in the study, or the vaccine supply is exhausted. In the event that the eligibility criteria are not met, the subject may be re-evaluated if the Principal Investigator anticipates that the research participant may meet the eligibility criteria later. As of Amendment #9, participants will be switched to annual vaccinations (+/- 30 days). If eligibility is later established, a new anniversary date for vaccine boosting and long-term follow-up will also be set as the date of the most recent vaccination.

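### Feasibility of priming and boosting in vaccine-naive patients is to be judged only by first-dose DLTs, a measure that cannot show whether the primes and a boost are delivered

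*Combined protocol and SAP*

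**What the plan says.** Section 4.1 names safety and feasibility of vaccine boosting as the primary statistical endpoint. For the naive cohort, the Study Synopsis says that "the feasibility of investigating the use of vaccine priming and boosting to prolong disease free status will be tested". Section 4.1 says that these patients "will be given three priming vaccines each a month apart, followed by semi-annual vaccine boosts in order to determine the feasibility of administering" (the object being vaccination of naive patients). As of Amendment #9, boosts become annual.

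The measure follows in the same section: "We will base our determination of feasibility by estimating the proportion of patients with a dose limiting toxicity (DLT) within 28 days", counted from the first vaccine. The only decision rule uses the same window. The concern that triggers it is worded "If there is significant evidence that more than 10% of the vaccine naïve patients have dose limiting toxicities within 28 days", again counted from the first vaccination, and the action is that "we will halt the trial due to excessive toxicity at the interim analysis if 6 or more patients have a DLT" in that period.

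Section 4.2 adds the DLT proportion within 28 days for each vaccination round, by cohort, with an exact 95% CI. Section 4.3.1 plans Kaplan-Meier estimates of recurrence-free survival from the first vaccine. No section defines the proportion of naive patients who complete priming or who reach a first boost.

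**The concern.** The aim concerns a sequence of at least four vaccinations spread over many months. The measure looks at one vaccination for 28 days. A patient who tolerates prime #1 and then withdraws, recurs, or fails the boost criteria counts exactly like a patient who receives everything.

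Such losses are built into the design. Section 3.4.6 takes patients off study for recurrence, exhausted vaccine supply, non-compliance or withdrawal. Sections 3.2.4 and 3.2.5 re-apply performance status, laboratory and no-recurrence criteria before each boost. None of these events is a DLT.

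Section 4.1 reports no DLTs in the phase I and II studies, so the feasibility measure is likely to come out near zero. The trial could then finish with a precise statement about first-dose toxicity and no planned estimate of whether the prime-and-boost schedule can be given, although that question is part of its stated primary statistical endpoint.

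**Working it through.** **1. The plan's own figures.** The exact (Clopper-Pearson) 95% CI for 6/20 is 11.89% to 54.28%, which matches the stated lower bound of 11.89%. For 5/20 the lower bound is 8.66%, so 6 is the correct cut-off for excluding 10%. The maximum normal-approximation width is 2 × 1.96 × √(0.25/n):
- n=20: 0.4383 (stated 0.438)
- n=40: 0.3099 (stated 0.309, truncated)

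The stated numbers are sound. The issue is what they measure.

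**2. Measurement window against schedule.**

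| Event | Time from prime #1 | Source |
|---|---|---|
| DLT window closes | day 28 | 4.1 |
| Prime #2 | day 28 ± 3 | 3.4.1.2 |
| Prime #3 | about day 56 | 3.4.1.3 |
| First boost, 6 months after prime #3 | about 7.8 months | 3.4.1 |
| First boost, 12 months after last vaccine | about 13.8 months | 3.2.4 |

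Here 56 days is 1.8 months, and 1.8 + 6 = 7.8; 1.8 + 12 = 13.8. The window ends before prime #3 and before either possible boost time.

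**3. What the DLT results can say.** The probability of not halting is P(X ≤ 5) with X ~ Binomial(20, p):
- p = 5%: 99.97%
- p = 10%: 98.9%
- p = 20%: 80.4%

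With 0/45 DLTs the exact upper limit is 7.9%. None of these figures contains a delivery term. They are the same whether all patients or one in ten reach a boost.

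**4. Whether another analysis fills the gap.** The per-round DLT proportions in Section 4.2 concern patients vaccinated in that round, so those who never reach it leave the denominator. The recurrence-free survival analysis in Section 4.3.1 captures recurrence. It does not capture refusal, ineligibility for other reasons, or supply.

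**5. Possible size of the loss (illustration).** Input: 6/14 disease-free at one year in phase I (Section 2.7.3), exact 95% CI 17.7% to 71.1%. Assumptions: the rate applies from the first vaccine, and the hazard is constant. Recurrence before a boost at t months = 1 − S^(t/12), where S is the one-year rate.

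| S | t = 7.8 | t = 13.8 |
|---|---|---|
| 6/14 | 42% | 62% |
| 71.1% | 20% | 32% |
| 17.7% | 68% | 86% |

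With an assumed exponential median of 12 to 36 months instead, recurrence would be 36% down to 14% at 7.8 months, and 55% down to 23% at 13.8 months.

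**6. Precision of a delivery proportion at the planned size.** The maximum exact 95% CI width is 0.456 at n=20, 0.324 at n=40 and 0.305 at n=45. Illustrative counts: 18/45 gives 40% (25.7% to 55.7%); 36/45 gives 80% (65.4% to 90.4%). No extra patients are needed.

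**The case against.** **A narrower aim.** The primary objective in the Synopsis and the primary endpoint in Section 4.2 are safety alone. Section 4.1 speaks of administering the vaccination to naive patients, and states openly that it will read feasibility as toxicity. On that view the plan made a choice rather than an error. This stands in part: the safety analysis is unaffected. But Section 4.1 itself puts feasibility of boosting in the primary statistical endpoint, and a first-dose measure is silent on boosting.

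**Later doses are not ignored.** Per-round DLT proportions are planned, their denominators would reveal how many patients received each dose, and recurrence from the first vaccine will be estimated. This is true, and it means the raw information will exist. It is not planned as a delivery proportion with a fixed denominator, a CI and reasons.

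**Declaring a failed regimen feasible.** A reader might infer that the plan would do this. The documents do not support it: Section 4.1 estimates a proportion and gives one halting rule, and no result triggers a feasibility verdict.

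**Most patients never reaching a boost.** A reader might also infer this. It is a possibility only. The 6/14 rate runs from diagnosis, comes from 14 patients of whom nine received lower doses (Section 2.7.1), and does not describe patients who must be recurrence-free at least 28 days after surgery and any adjuvant therapy. At 7.8 months the central figure is below one half. The documents do not say whether any naive patient's first boost fell under the annual schedule.

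**Eligibility.** Section 3.2.1 says it is not re-evaluated for primes 2 and 3, so that source of loss applies to boosts only.

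**Conclusion.** The point holds as a mismatch between aim and measure. The proportion with a DLT within 28 days of the first vaccine is a valid first-dose safety estimate, and the halting rule built on it is correctly calculated. Neither can inform the feasibility of priming and boosting, and no other planned analysis measures delivery of the regimen.

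This conclusion needs no assumption; it follows from the timing in Sections 3.4.1 and 4.1. The size of the loss before a first boost does rest on assumptions and is unknown. Recurrence alone could plausibly remove anything from a modest minority to a large majority, depending on the underlying rate and the boost interval. No figure can be given for refusal, other ineligibility or supply, because the documents offer none.

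The change should be made: part of the stated primary statistical endpoint would otherwise go unanswered. Patient protection and sample size are not affected.

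**What to change.** In Section 4.1, keep the 28-day DLT proportion and the halting rule, and label them as safety. Base feasibility in the naive cohort on two proportions, each with all naive patients given vaccine #1 as denominator and an exact 95% CI:

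1. received all three primes;
2. received all three primes and a first boost.

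Tabulate the reasons for non-receipt: recurrence, toxicity, other ineligibility, refusal or withdrawal, vaccine supply. Separating recurrence from the rest keeps an efficacy matter distinct from practical delivery.

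Count a dose as received regardless of delays that the protocol permits. A timing window cannot be applied yet. Section 3.4.1 and Section 3.2.4 give different boost intervals, Section 3.2.1 allows a three-week delay, and Section 3.2 allows a boost to be deferred for up to one year after a vaccine-related response. These passages must be reconciled first.

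The documents state no minimum acceptable delivery rate, and the two proportions remain estimates without one. If the sponsor wants a verdict on feasibility, it would have to set that minimum in advance.

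The cost is SAP wording, two proportions and one table from vaccination and off-study records. The downside is a little more analysis and a feasibility result that may look less favourable.
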